Getting Healthy is a 7-module website with interactive features aimed at reducing cardiovascular risk through healthier lifestyle choices. Modules are: Nutrition Center, Physical Activity, Healthier Kids, Weight Management, Stress Management, Quit Smoking, and Workplace Wellness. Each of the modules has a separate URL. Participants can sign up for a monthly e-newsletter. Getting Healthy does not have its own dedicated online community. We will e-mail a link to a new module weekly in order to parallel the seven weeks of PSFW+ sessions, and will send two email reminders and one text (if the subject agrees to receive text messages) weekly to prompt users to visit the module, as well as a reminder phone call after 10 days of non-use to parallel the adherence protocol in the PSFW+ condition. We estimate that each module will take an average reader 15-30 minutes to complete which corresponds closely to the time requirement for PSFW+ written content. Legacy will create a “portal page” that will require control participants to log in, generating data regarding website use. At the time of enrollment, the research assistant will introduce the participant to the portal page. Following entry of a unique username and password that will be assigned during enrollment, participants will be routed to the Getting Healthy module of the week. This approach will optimize attention matching and will also allow the team to collect basic Getting Healthy utilization metrics.]]

PSFW+: Positively Smoke Free on the Web plus Online Social Network PSFW+ participants will be registered on the website by the research assistants following randomization. Each participant's unique Study ID will be tied to his/her website registration to enable linkage of website utilization metrics with other data collected during the trial. Registration involves creating a username and password, entering an email address, and a mobile phone number (if available). The participant will receive a confirmation email following registration that contains a link to the site and instructions to bookmark it in his/her Internet browser for easy access.

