Social Cognitive Theory,⁹³ content focuses on providing information, increasing motivation to quit, and increasing self-efficacy to resist smoking temptations (**Table 2**) via presentation of objective data as well as hypothetical “real world” scenarios of particular relevance to PLWH smokers. Users are given tools and options to cope with smoking urges. NRT use is encouraged. **Online social network:** The PSFW+ community runs on open source forum software by Vanilla Forums. We created a full-featured discussion forum with unlimited categories and user profiles that is customized to look like the main site. Vanilla Forums enables single sign-on for a seamless experience between the static content and online community. PSFW+ users can create a user profile with a unique avatar or personal photo, and can create a profile “wall” on which other users may post comments, images, or video. The primary interface is a feed of discussion threads: users create discussions or polls, and other users may post comments to the discussion or answer the poll. Users can also exchange private messages. The **PSFW+ Community Guidelines** emphasize the importance of creating and maintaining a safe environment for people to exchange information and support. The guidelines also remind users that all content posted in the community is publicly available, and that the administrator may remove messages that are spam or solicitations. Users who persistently violate Community Guidelines will have their community profile removed from the site. Our experience with several online communities with thousands of users is that these occurrences are infrequent; should they occur during the study period, we will account for this in our analyses. Involvement of an experienced administrator is integral to managing these situations proactively to ensure the smooth operation and success of an online community,^{24,94} especially during its nascent phase. The **PSFW+ Community Administrator** will monitor all public discussions and comments on the community, encourage interactions between community members, review all reports of inappropriate content that do not follow the Community Guidelines (such as spam), and serve as the main liaison between technical staff and community members for any technical issues. The **PSFW+ Terms of Use** and **Privacy Policy** make explicit that all content posted in the community is publicly available information and users are legally responsible for any content they post on the site. The registration page states “By clicking Submit, I agree to the Positively Smoke Free Terms of Use and Privacy Policy” (available via hyperlink). The treatment of the unique privacy concerns of a PLWH online community and its attendant legal implications have been carefully considered and are discussed in detail in the Human Subjects section.

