
A critical mass of 10 or more seed users will be retained on contract to ensure that active dialogue within the community is maintained. Seed users will be responsible for posting daily on at least 15 days a month, starting new discussions, and responding to posts in existing ones. As PSFW+ enters the public domain, we will promote the site nationally to PLWH smokers through posts on a variety of HIV/AIDS social support groups and related non-profits on social networking sites, and outreach to a national health communications listerv.

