Additional Control and Evaluation Measures: Other treatment exposure: Using standard assessment items administered in previous trials,¹⁴³ we will assess use of other cessation treatments including alternative smoking cessation websites, non-study NRT, prescription medications (e.g. varenicline), behavioral treatments (pamphlet/book, live and/or telephone counseling), and alternative quit methods (e.g., acupuncture, hypnosis). Individuals who report use of cessation websites will be asked to identify each specific website and the number of visits. [[Information about membership in any other health-promoting or tobacco treatment online communities will be collected from all subjects.]] **Treatment Satisfaction Questionnaire:** PSFW+ participants will be asked the number of times they visited the website, the approximate length of each visit, and ratings of overall satisfaction and perceived helpfulness of the site. Participants who report that they did not visit the website will be asked for specific reasons for non-use (e.g., lost Internet access, lack of interest, etc.). Similar questions will be asked regarding the Getting Healthy website. Additional questions will address knowledge of and familiarity with PSFW+ and Getting Healthy; these questions will be designed to detect potential study contamination. **PSFW+ Utilization Metrics:** We will extract the following utilization variables: date/time of registration, # site visits, date/time of each visit, # page views, date/time of each page view, # page views per session, # interactive component clicks, changes to personal profile (e.g., email, username), whether the user signed up for text messages, # text messages sent, and # emails sent to participant from the system. We will also extract the following variables from the Vanilla Forums database specific to community utilization: # clicks through to the community from PSFW+ content pages, # direct visits to the community, # discussion posts, # comments, # private messages sent/received, # wall posts made/received, and whether or not they customized their profile (e.g., photo). Getting Healthy utilization metrics will rely on data collected from the portal page (3.C.4.e.) and subjects' historical recall. At the end of Visit 2, we will administer the 18-item Sense of Virtual Community scale to PSFW+ participants.

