[[3.C.6.e. Sample Size Considerations: Aim 1. Using the mean abstinence rates in the SC arms in our two recent R21 trials (9.7%²¹ and 4.3%¹⁴), and up-adjusting the rate slightly in consideration of the attention-placebo, we estimate a 7-day ppa at 6 months in the control condition will be 7.5%. Our estimate of the efficacy of PSFW+ is based on research by our team²⁰ and others⁶² who have demonstrated that visits to an online community increase abstinence rates. In the BecomeAnEX outcome evaluation,²⁰ 7-day ppa at 6 months ranged from 11.1% (ITT) to 20.7% (responder only); individuals who visited the online community two or more times were more than twice as likely to be abstinent than those who never visited (OR=2.22, 95% CI 1.34-3.69, P=.002) controlling for a broad range of demographic, smoking, and psychosocial covariates. These results are consistent with An et al.⁶² who reported a near doubling of abstinence rates (OR=1.91) among individuals who used individual messaging in an online cessation program. The benefits of an online community are not simply for the minority who actively post; reading communications ("lurking") also has beneficial effects.^{150,151} Therefore, we estimate that PSFW+ combined with our intensive adherence strategies to promote engagement and utilization will increase abstinence rates by 2.05 times over control, yielding a 6-month quit rate of 15.4%. This estimate is deliberately conservative in that we have chosen to use as the base rate our estimate of control (7.5%) rather than the quit rate from our previous trial of PSFW (10.1%). This will ensure that we are adequately powered to detect treatment group differences between PSFW+ and control. Assuming abstinence rates of 15.4% and 7.5% in the PSFW+ and control conditions, respectively, 254 subjects in each arm will be necessary to achieve power of 0.8 with an alpha=0.05. Projecting a liberal 9.2% loss-to-follow-up based on our previous NIH-funded trials (R21CA163100-01, R21DA023362), we will randomize N=275 per arm.]]

Sample Size Considerations: Aim 2. We are able to detect a mediation effect (coefficient product) of small size

(with coefficient product parameters $a=0.14$, $b=0.14$) with at least 80% power for each mediator given our expected sample size of $N=508$ at 6 months.¹⁵²

3.C.7. Potential Problems and Solutions

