Subject Attrition. Loss to follow-up will be minimized through the use of standard tracking/contact sheets, reminder calls/emails/texts, incentives linked to follow-up completion (\$30 cash each visit), and provision of travel fare for all study visits. We will emphasize that incentives are not dependent on website usage or on abstinence, but rather on completion of study visits. Retention rates have been high in our previous clinical trials: during 7 years of participation in Community Programs for Clinical Research on AIDS (CPCRA) trials, MMC ranked in the top 3 sites nationally for retention, losing <2% of subjects from long-term follow-up. Retention rate within various clinical trials (e.g., ACTG, WIHS, HPTN) at MGUH are also impressively high (98%). The aggregate loss to follow-up rate in the three tobacco treatment RCTs conducted in the MMC ID Clinic has been 4.8%.

Study Condition Contamination. To prevent contamination (i.e., subjects accessing non-assigned study websites), we will record control participants' email address at the time of study enrollment in a database linked to the PSFW+ data store. Control participants who attempt to register on PSFW+ using a recorded email address will be redirected to the welcome page of the Getting Healthy site. It is also conceivable that control subjects will register on PSFW+ with a different email address. We will probe for this occurrence and for PLWH+ utilization of the Getting Healthy website in the Treatment Satisfaction Questionnaire at follow-up and will adjust the analyses accordingly.

Generalizability. Once efficacy is established in this controlled trial with optimal recruitment and in-person assessment protocols, future dissemination studies will be conducted that will prioritize external validity.

3.C.8. Timeline and Benchmarks for Success: **Months 0-9:** Modifications and enhancements to PSFW+ including adherence prompts, technical strategies to minimize contamination, efforts to grow and evaluate online community, refinement of assessment protocols, programming of ACASI systems. **Months 10-54:** Recruitment and follow-up at 1, 3- and 6-months, with the final follow-up in Month 54. Preliminary data analyses will be conducted throughout the project.

Months 55-60:

Final outcome analyses and manuscript preparation.

Benchmarks for success:

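### The only access block keeping controls off PSFW+ is a match on one recorded email address, and the sample size has no allowance for crossover that could dilute the 6-month contrast

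*Combined protocol and SAP*

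**What the plan says.** Section 3.C.7 (Study Condition Contamination) describes one barrier. Controls' email addresses are stored at enrollment in a database linked to PSFW+, and "Control participants who attempt to register on PSFW+ using a recorded email address will be redirected" to the Getting Healthy welcome page. The protocol then accepts that a control could sign up under another address. Its response is to ask about this in the follow-up satisfaction questionnaire and to adjust the analyses, with no method named.

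Other sections bear on how easily controls could reach the content:

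- Section 3.C.4.e says the Community Guidelines remind users that "all content posted in the community is publicly available".
- The same section says: "As PSFW+ enters the public domain, we will promote the site nationally to PLWH smokers". Section 3.C.1.g also plans promotion during start-up.
- The PSFW+ registration form (3.C.4.e) asks for an email address and, optionally, a mobile number.
- Section 3.C.5 says: "Additional questions will address knowledge of and familiarity with PSFW+ and Getting Healthy", in order to detect contamination. It does not say at which visit.

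Section 3.C.6.e sets the sample size: "Assuming abstinence rates of 15.4% and 7.5% in the PSFW+ and control conditions, respectively, 254 subjects in each arm will be necessary". The target there is 80% power at the 5% level. It then randomizes 275 per arm to cover losses. The effect-size argument there counts people who only read posts among those who benefit.

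**The concern.** The block acts at registration, and only on one identifier. It does not stop a control who uses a second address. It would not stop reading at all if threads are open to visitors who have not logged in. The protocol treats reading as part of what works, so exposure without registration matters.

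Controls also have reason to look. They must be motivated to quit within 30 days and be online at least weekly (3.C.4.b). Their assigned site has a single tobacco module, scheduled for week 6 (Table 1).

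If PSFW+ works and some controls use it, the control quit rate rises and the Aim 1 difference shrinks. An effective program could then be judged ineffective. Crossover by month 3 would also narrow the difference in the social support mediator for Aim 2, which is measured at that visit (3.C.6.c).

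Adjusting afterwards for self-reported use cannot restore the lost contrast. Conditioning on behavior after randomization also gives up the protection that randomization provides.

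**Working it through.** **Inputs from section 3.C.6.e.** PSFW+ rate 15.4%; control rate 7.5%; 254 per arm needed; 275 per arm randomized; power 0.80; alpha 0.05 (sidedness not stated).

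**Inputs assumed.** The crossover share *x* and the fraction *b* of the PSFW+ benefit that a crossed-over control gains. The documents give neither.

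**Step 1: reproduce the plan.** With pooled variance, two-sided 5% and no continuity correction,

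n = [1.960·√(2p̄q̄) + 0.8416·√(p₁q₁ + p₂q₂)]² / (p₁ − p₂)²

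where p̄ = 0.1145 and p₁ − p₂ = 0.079. This gives

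n = [1.960 × 0.4503 + 0.8416 × 0.4468]² / 0.006241 = 253.8, so 254.

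The plan's figure is reproduced exactly. A one-sided test would give 200, and a continuity correction 279. Power at 254 is 80.0%, so nothing is held in reserve for crossover.

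**Step 2: dilute the control rate.** Control rate = 7.5% + x·b·7.9 points. At x = 10% and b = 1 this is 7.5 + 0.79 = 8.3%, leaving a difference of 7.1 points.

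**Step 3: recompute power** = Φ{[d√n − 1.960·√(2p̄q̄)] / √(p₁q₁ + p₂q₂)}. At x = 10%, b = 1 and n = 254:

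(0.0711 × 15.94 − 1.960 × 0.4570) / 0.4542 = 0.523, so power is 69.9%.

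Full benefit in crossovers (b = 1):

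| Crossover | Control rate | Difference (points) | Power, 254 per arm | Power, 275 per arm | n per arm for 80% |
|---|---|---|---|---|---|
| 0% | 7.5% | 7.9 | 80.0% | 83.1% | 254 |
| 2% | 7.7% | 7.7 | 78.2% | 81.3% | 266 |
| 5% | 7.9% | 7.5 | 75.2% | 78.5% | 286 |
| 10% | 8.3% | 7.1 | 69.9% | 73.4% | 324 |
| 20% | 9.1% | 6.3 | 58.5% | 61.9% | 421 |

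Only the product x·b matters, so half benefit is read from the row at half the crossover. At 10% crossover and b = 0.5, power is 75.2% (254) or 78.5% (275).

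The 275 column applies if the planning rates are intention-to-treat rates, because section 3.C.6.b counts participants who miss the 6-month visit as non-abstinent and so keeps everyone in the analysis. In that column power falls below 80% somewhere between 2% and 5% full-benefit crossover.

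**The case against.** **There are other safeguards.** Spouses, partners, roommates and prior PSFW+ users are excluded (3.C.4.b). Section 3.C.8 schedules technical strategies against contamination in months 0 to 9. Section 3.C.5 asks everyone about other cessation websites and online communities. This stands, but the exclusions do not stop an enrolled control from finding the site, the technical strategies are not described beyond the email redirect, and the questions detect crossover without preventing it.

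**Public availability may be only a warning.** The phrase comes from guideline and terms-of-use language about privacy and liability. Username and password registration, single sign-on and individual visit tracking suggest that reading may already need a login. This stands as a limit. The documents never say whether unregistered visitors can read threads, so open reading cannot be assumed.

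**Full benefit is close to a worst case.** Section 3.C.6.e ties the 15.4% to PSFW+ together with intensive adherence strategies. A control reading covertly would not get the PSFW+ outreach calls, and over 94% of pilot participants needed at least one (3.C.1.e). This stands, and is why the half-benefit figures are given.

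**Promotion is deliberate.** A working community needs members (3.A.5.b), and a login requirement could reduce outside readership. This is a real cost.

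**Conclusion.** The point holds as a risk of unknown size. One identifier guards access, the protocol itself names the gap, and the sample size has no allowance for crossover. With full benefit in crossovers, power is 75% at 5% crossover and 70% at 10% with 254 per arm (78.5% and 73% with 275). With half benefit, 10% crossover gives 75% (78.5%). The crossover shares and benefit fractions are assumptions.

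A reader might infer more than the documents support:

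- *That the contrast is diluted.* No crossover rate is given, so it can only be said that it could be.
- *That the contamination questions tip controls off before month 6 and should be delayed.* The visit is not specified. Consent already covers both conditions (5.B) and prior PSFW+ use is an exclusion that has to be screened, so delay would remove little awareness. It would also lose dated crossover data.
- *That wider use of PSFW+ would starve recruitment through the prior-use exclusion.* Section 3.C.4.c gives about 1,950 + 780 = 2,730 smokers, plus more than 500 new patients a year, for 550 places. Nothing suggests that the exclusion would bind.
- *That crossover could produce a false positive.* It biases toward no difference and does not inflate type I error.

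**What to change.** Until the last participant's 6-month visit:

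1. Match new PSFW+ registrations against control participants' mobile numbers as well as their emails. The form already asks for a number, and the control reminder calls and texts require contact numbers.
2. Require login to view sessions and community threads, if that is not already so, and state the rule in section 3.C.4.e.

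In sections 3.C.6.b and 3.C.7:

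3. Replace the open promise to adjust with a rule: the primary intention-to-treat comparison is not adjusted for crossover after randomization, crossover is reported by arm, and a sensitivity analysis for crossover is specified in advance.

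The cost is one extra matching field, a forum permission setting and a few lines of text. Outside visitors would have to register to read. Phone matching will be incomplete because the number is optional. No extra participants are needed. The appended 2021 amendment says the parent trial closed in 2020, so items 1 and 2 concern the plan as written, while item 3 can still govern how results are reported.

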Adults	Female	0	7	222	36	89	0	354
	Male	0	17	485	84	223	0	809
Children	Female	0	0	15	0	0	0	15
	Male	0	0	22	0	0	0	22
Total		0	24	774	120	312	0	1200

* Transgender individuals (approximately 1% of the overall population) are included in the gender statistics with which they self-identify.

Inclusion Criteria: We will recruit N=550 adult PLWH smokers. Inclusion criteria are: 1) age 18 or older; 2) current smoking as defined by a validated tobacco use measure; 3) laboratory confirmed HIV-infection; 3) receipt of care at either MMC or GUH study site; 4) English language fluency; 5) motivation to quit within the next 30 days; 6) at least weekly Internet and email access; 7) REALM literacy score of 19/66 or above, indicating reading level of at least 4-6 grade (PSFW content was written for this literacy level); and 8) willingness to provide informed consent and undergo randomization.

Exclusion Criteria: 1) previous participation in any trial of Positively Smoke Free interventions or use of PSFW+; 2) pregnancy; 3) contraindication to NRT; and 4) current participation in an active smoking cessation treatment (e.g., group therapy, use of pharmacotherapy). PSFW+ seed users will be excluded. To avoid study condition contamination and to maintain the statistical independence of subject outcomes, otherwise eligible individuals who are

spouses, partners, and/or roommates of study participants will be excluded. All ineligible patients will receive a Positively Smoke Free smoking cessation brochure and will be encouraged to access nationally-available (free) quitline counseling.

Inclusion of Women and Minorities: With the exception of pregnant and nursing women, women will be fully included in the study. The safety of NRT has not been established in pregnant women or women who are breastfeeding. Furthermore, pregnant women smokers should be referred for aggressive smoking cessation interventions with proven efficacy, so allocation to the control condition would conflict with best care practices. The exclusion of women who are breastfeeding is of little practical significance since breastfeeding is contraindicated in HIV-infected women in the US. The vast majority of the aggregate clinic populations belong to ethnic minority groups, and the investigators expect the study cohort to reflect the ethnic makeup of the clinics. Asian and Pacific Islanders and Native Americans will be fully eligible for enrollment but are unlikely to comprise a numerically important subset of the study sample because they make up less than 3% of the clinics' populations.

Inclusion of Children: Clinic patients aged 18 to 20 will be eligible for inclusion in the study. A small number of individuals in this age range typically attend the clinic site each year as they transition from pediatric/adolescent care settings. There were no children in the MMC ID Clinic population in 2013, although a small number are expected to transition from the adolescent clinic in future years. Younger children and adolescents have smoking-associated behaviors and risks that differ from those of the adult population. For younger children, the primary medical concern is exposure to environmental cigarette smoke. Adolescent smokers typically smoke fewer cigarettes than adults, with more irregular patterns of cigarette consumption. Because of these significant behavioral differences, and because they receive care in separate facilities, we will not include younger children or adolescents in the proposed project.

Randomization: Following referral from primary care providers, research staff will conduct eligibility screening and informed consent. Once consented, the participant will be randomized to one of the two study conditions. Based on strong predictors of smoking behaviors that emerged in our prior work, randomization will be stratified by gender and education level within each clinic. An online random plan generator (<http://www.randomization.com>) will be used to create an allocation schedule. The schedule will be fully documented with the reference citation of the pseudo-random number generator, the seed used to start the generation process, the number of study conditions (2), the allocation ratio (1:1), and a copy of the assignment list.

Collaborating Sites: [name] (MPI) at Westat will oversee the conduct of the study at Georgetown which is in close proximity to her worksite and with which she maintains an ongoing affiliation. The Georgetown site will recruit participants from the MGUH HIV Clinical Program. [name] will be responsible for recruitment and follow-up at this site, and [name] will oversee the overall conduct of the study at Georgetown. Montefiore Medical Center (MMC) will recruit patients from the MMC Infectious Diseases (ID) Clinic in the Bronx, NY. [name] from MMC will serve as MPI and provide expertise in HIV care and tobacco treatment. [name] and her software development team at the American Legacy Foundation will be responsible for delivering the PSFW+ intervention. They will be responsible for administering the online community and for developing and monitoring the automated tracking metrics on website utilization.

Sources of Materials

Specimens, Records, or Data: Enrolled subjects will complete measures (**see Table 2**) in a private office using an ACASI interface on a password-protected study computer. Study staff will be nearby to render any assistance necessary. Input data will be maintained on the computer's hard drive and will be uploaded on the day of questionnaire completion via a secure Sharepoint portal to the AECOM Epidemiology Informatics/Study Management Unit (EISMU - please see Protection of Study Data below and the AECOM Resources section). Exhaled carbon monoxide measurements will be performed according to manufacturer's instructions and discordant abstinence data (frequently observed in marijuana users) will be clarified with saliva cotinine strips. Biochemical validation results will be keyed by study staff into the study databases. All locally maintained computer data will be stored on password protected computers/servers and backed up to encrypted Ironkey USB drives.

Website utilization metrics will be extracted from the back end of the PSFW+ intervention. These metrics include 1) an event tracking database within the PSFW+ application for non-community related actions, and 2) community related data from the Vanilla Forums database. From the event tracking database within the PSFW+ application we will extract individual-level metrics utilization including the date/time of each session and page visited, date/time of each site login, the referring URL for each site visit, the date/time of registration, number of clicks through to the community (date/time stamped), number of page views per session (date/time stamped), number of interactive component clicked (date/time stamped), and changes to profile such as email or username. We will also track the number of email and text messages sent to each participant as a function of the individually tailored adherence strategies we will employ for this study. From the Vanilla Forums database, we will extract individual-level tracking metrics including (among others) visits, number of discussions participated in, number of comments made, number of private messages sent/received, number of profile posts made/received, and whether a custom profile photo was uploaded.

For subjects in the control condition, time and duration of each login to Getting Healthy via the portal page will be recorded. Email and text message reminder data will be compiled in the same manner as the PSFW+ condition.

Materials Access: During the course of the project, the Investigators, Data Analyst, Software Development Team, Community Administrator, and Project Manager will have access to individually identifiable information about human subjects. In addition, Vanilla Forums technical and support staff will have access to registration data and any data arising from participation in the online community. This access is detailed in the Vanilla Forums Terms of Service and Privacy Policy which are referenced in the PSFW+ documents. The Getting Healthy website will have access to users' IP addresses, but these users will not be distinguishable from any other user of the AHA Getting Healthy site. These various levels of access will also be listed in the participant informed consent document.

Protection of Study Data: All data in transit will be transmitted with security precautions. Data moving between application server and database or other data stores will be secured via Secure Socket Layer (SSL). Data from the PSFW+ application database will be transferred to Legacy's local servers via direct SSL connection with the database and stored on secure servers with restricted access rights. Data from the Vanilla Forums community software will be transferred to Legacy's local servers via SFTP ("Secure File Transfer Protocol" or "FTP over SSL"). Personally identifiable data (e.g. phone number, email address) associated with the PSFW+ application will be encrypted in the database.

Each subject will be assigned a unique, randomly-generated study identification number by clinic staff. This number will populate the key index field in the relational database structure. The MGUH and MMC ID Clinic research staff will maintain a secure database that links the study number with patient identifiers. For participants randomized to the PSFW+ condition, research staff will enter this study identification number into the website registration form which will be stored by Legacy. For those in the control condition, the identification will populate the back-end table of the Getting Healthy portal page. This will enable individual tracking of study participants and linking of website utilization metrics to other study data by StudyID. The Principal Investigators, research staff, and software development team will have access to individually identifying information about human subjects. Electronic data files with identifying information will be maintained securely and separately from other data files.

The ACASI questionnaire result uploads will contain the participant's unique study ID number, but no other personally identifying information. For these data the EISMU has implemented a comprehensive Security Program that conforms to the National Institute of Standards and Technology (NIST) standards and the EISMU official Certification and Accreditation documentation has been accepted by the NIH. The EISMU provides secure data hosting, access and backup services and data security provisions are applied systematically at multiple levels to ensure safe and accountable data storage and access. Multiple factor authentication is required for access to critical systems which include login and password authentication, individual token verification and IP address restrictions. The system complies with HIPAA requirements and utilizes a Secure Socket Layer certificate to ensure data encryption during data transmission. Servers maintain audit logs of all connections and data modifications with access to users granted after certification criteria are met. A fully virtualized environment, built on Dell's hardware and VMware's enterprise level hypervisor, is utilized to provide high performing and highly available systems. Advanced backup and

recovery systems are implemented to protect both complete server images and file level data. Redundancy is built into the infrastructure at various levels to minimize downtime in the event of an unexpected system failure including RAID disk arrays, bonded network interfaces, clustered VMware hosts, and file level replication. Cisco firewalls are used to protect all mission critical servers. Symantec Backup Exec and VMware Data Recovery are implemented as an enterprise backup/restore system. Critical database information is backed up at regular intervals to ensure minimal data loss in the event of a catastrophic disaster and to allow for both quick restoration of entire servers, as well as granular restoration of critical files. On site and off site backups include backups to disk (storage area network) and tape. A Virtual Private Network is available for remote access. The system employs a defense in depth model to safeguard data ensuring that only authorized users can access the network resources.

All personnel will receive certification in human subjects protections from the NIH Office of Human Subjects Research prior to beginning work on this project. Outside parties who may be afforded access include designees of the Institutional Review Board overseeing the study site and the National Institutes of Health and Department of AIDS.

Potential Risks

We anticipate four potential risks for participants in this study, though it is important to stress that the overall risk is judged to be low. **(1) Nicotine withdrawal symptoms:** Study participants who attempt to quit smoking will likely experience some withdrawal symptoms that may include anxiety, restlessness, anger, irritability, sadness, problems concentrating, appetite change and weight gain, insomnia, and decreased heart rate. There is no reason to believe that participation in this study would worsen nicotine withdrawal symptoms or that symptoms would differ based on randomization assignment. **(2) Breach in data-related confidentiality/privacy precautions or through self-disclosure of personal information in an online social network:** Breach in privacy or confidentiality may occur related to data collection, storage, or transit, or via personally identifiable information posted by study participants in the PSFW+ community. **(3) Emotional distress:** Participants may experience emotional distress consequent to the data collection process since assessment measures include questions about social support, loneliness, substance use, and psychiatric illness. Participants may also experience emotional distress subsequent to participation in an online community if conflicts should arise. **(4) Nicotine replacement therapy side effects:** More common side effects of the nicotine patch include local skin irritation at the site of the patch, nausea if the dose is too large or if the patient continues to smoke at a high level while using the patch, and disturbed and vivid dreams. Less common side effects include allergic skin reactions.

Alternative Treatments and Procedures

Alternatives to study participation include continuing to smoke and pursuing smoking cessation strategies outside of the study. Readily available and free cessation treatments will be described in the informed consent document.

5.B. ADEQUACY OF PROTECTION AGAINST RISKS

Recruitment and Informed Consent

PLWH smokers without contraindications to NRT will be referred by their primary care providers to the study staff who will be present in the clinic to screen and then enroll patients or schedule an enrollment visit. Primary care providers will be alerted to the study through provider staff meetings, study flyers, and presentations at Community Advisory Board meetings at both clinics. In the event we do not meet accrual goals, research staff will directly recruit patients in clinic waiting areas. MMC and MGUH both enjoy collegial academic relationships with nearby HIV-care centers caring for thousands of additional PLWH smokers, and these may serve as secondary referral sources if the need to augment recruitment arises. Study staff will screen referred patients to determine eligibility. Individuals who are not eligible for the study will receive the Positively Smoke Free smoking cessation brochure. Eligible patients will complete the informed consent process in a private room in or nearby the clinic. The informed consent document will describe the randomized trial, including the possibility of being assigned to either of the study conditions and the right to withdraw at any time. All aspects of the study, including the informed consent document and process, will be approved by the governing IRB prior to study recruitment. Subjects will be provided a copy of the completed informed consent document, the original will be placed in each subject's case report form, and a copy will be placed in a

dedicated section of each subject's medical record.

Protections Against Risk

(1) Nicotine withdrawal symptoms: All participants will be offered nicotine replacement therapy which is intended to reduce withdrawal symptoms. Worsening of depression and/or anxiety as a result of nicotine withdrawal is addressed in item 3 of this section.

